NCT06742047
A PROFESSIONAL DEVELOPMENT
PROGRAMME (PRODEVELOP)
FOR NEWLY GRADUATED NURSES 2023

Summary

Pre-specified study protocol and statistical analysis plan (SAP)
Update review 2026-02-18
Project Leader
[name], Professor

[name]
[contact]

Sustainable Professional Development – Introduction Program for Newly Graduated Nurses

1. Background

A newly graduated nurse (NGN) entering their first workplace may experience significant uncertainty and considerable stress. Common stressors include being exposed to challenges such as work overload and feeling alone and uncertain in the new situation (Duchscher, 2012). Studies show that one-fifth of NGN reported frequent symptoms of burnout, and an equal number had thoughts of leaving the profession (See et al., 2023). In Region Västmanland, 20% of newly hired nurses leave their first position after three years. After three years, 42% remain in their first position (Törnqvist, 2020).

To support NGN in their transition to practice, healthcare organizations offer introduction programs and other initiatives intended to promote learning and integration, thereby creating a sustainable start in the profession. Previous research shows that such introduction programs for NGN can contribute to competence development, but they are not always based on scientific evidence (Rush et al., 2019). Earlier research on introduction programs for several professional groups, including NGNs, showed positive effects on perceptions of uncertainty and stress. Implications for continued development include creating more targeted interventions that promote role clarity, action capacity, recovery, and social acceptance (Frögéli et al., 2023).

Sick leave among nurses in Region Västmanland is currently around 7.5% of approximately 1,000 registered nurses, potentially related to stress and uncertainty in the profession. Many choose to leave the profession, placing additional strain on those who remain. Supporting sustainable professional development is therefore crucial. Creating, implementing, and evaluating an evidence-based introduction program may contribute to increased job satisfaction.

2. Interventions of ProDeveloP

In this project, a professional development program (ProDeveloP) is developed and will be implemented based on existing research in the field, particularly results from earlier research on sustainable working life focusing on new professionals such as NGNs (Frögéli et al., 2022; Gustavsson et al., 2020), funded by AFA. Based on these findings, ProDeveloP will be developed with targeted components with a special focus on reflection and recovery, which were specifically highlighted as needed (Widarsson et al., 2020), to optimize its effect and support job satisfaction and health among NGN. The project will be conducted in collaboration with Region Västmanland and Mälardalen University (MDU).

ProDeveloP was developed based on the previous introduction programme and existing research. ProDeveloP will be implemented in 2023 through a collaboration between a university and a regional education centre and will be conducted in Swedish. It consisted of eight educational days delivered over the first four months (the same as in the previous introduction programme in 2022), however also incorporated simulation exercises for acute and trauma situations, as well as skills training in various clinical procedures. It also included additional components such as four focus areas—role clarity, task mastery, social acceptance,

and recovery—and integrated structured reflection facilitated through dialogue groups, addressing ethical and emotional challenges.

3. Purpose and Research questions

The purpose of the project is to develop, implement, and evaluate a digital professional development program aimed at strengthening newly graduated nurses' role clarity, capacity for action, social acceptance, reduction of stress, and improvement of recovery, thereby increasing job satisfaction.

1. What does the development of role clarity, task mastery, social acceptance, and stress look like during the first quarter of employment?
2. What are newly graduated nurses' experiences of recovery, and how does it develop during their first year when participating in ProDeveloP?
3. What are their experiences of reflection sessions, supervisors, and support for professional development?
4. To what extent are newly graduated nurses satisfied with their work, feel confident in their competence, and want to remain in their workplace after completing the ProDeveloP?
5. What are supervisors' and managers' experiences of ProDeveloP?

4. Method

Research participants

All newly hired NGN participating in ProDeveloP will be invited to participate in the studies. Two groups (January 2023 and June 2023), each with 40–50 participants. One control group of NGNs participating in the prior introduction programme will be invited to participate in November 2022, with approximately 40-50 participants.

Design and Data Collection

The project has a prospective, longitudinal design. Both qualitative and quantitative methods will be used to answer the research questions. The questionnaires used in the study are based on validated instruments (Frögéli et al., 2019), which helps ensure the reliability of the data collected. The questionnaires will be distributed digitally via Survey and Report. One control group measurement is planned before intervention starts. Self-assessments via questionnaire are planned to be completed by the NGNs. Thereafter, self-assessments are conducted once a week during the first quarter for the intervention group. Follow-up measurements are then carried out once per quarter for up to one year after graduation. The individual interviews with NGNs and managers, and the focus groups with NGNs and supervisors, are planned to be conducted after the program has been completed. The qualitative interviews will be audio-recorded and transcribed. An overview is presented in Table 1.

Table 1. A detailed table of data collection and data analysis

Research question	Data collection	Data analysis
1	Self-assessment instruments	Descriptive statistics, regression analyses
2	a) Individual interviews b) Self-assessment instruments	a) Phenomenology b) Descriptive statistics, ANOVA, χ^2
3	Focus group interviews	Content or thematic analysis
4	a) Self-assessment instruments b) Individual interviews	a) Descriptive statistics, ANOVA, χ^2 b) Content analysis or phenomenography
5.	Focus group interviews and individual interviews	Content or thematic analysis

Timeline

Once the analyses and results have been completed and the journal editors have approved the publication; the results will be made public. Publications will take place continuously, but the doctoral thesis work is planned to be completed with a defence at the end of 2027.

Ethical Considerations

All NGN entering the introduction year will receive written and oral information about the project. Participation is voluntary and can be withdrawn at any time. A consent form will be provided. Data will be handled confidentially, and a data management plan will be prepared. An application is approved by to the Swedish Ethical Review Board (Dnr.2022-05682-01).

5. Pre-specified statistical analysis plan

The plan comprehends a statistical analysis plan for self-assessment instruments.

Study design and study population

A quantitative intervention design with a non-randomised design with a two-arm structure is planned. The study's first arm (control group) is all eligible NGNs who participates in the previous introduction programme in September 2022. The survey for this group will be administered in late November 2022. The second arm (intervention group) comprise all eligible NGNs participating in the ProDeveloP starting either in February or in September 2023, depending on their graduation date. The surveys for group comparison will be distributed digitally in early May or December, aligned with the same time frame as the control group. Longitudinal surveys will also be collected during the intervention group's first year in ProDeveloP however this is not possible for the control group.

Inclusion criteria were newly employed NGNs who participated either in the previous introduction programme in 2022 or in ProDeveloP in 2023. Specifically, all eligible NGNs employed in 2022 who participated in the September introduction programme were included in the control group. All eligible NGNs employed in 2023 who participated in ProDeveloP,

starting in either February or September, were included to the intervention group. No explicit exclusion criteria were applied.

Outcome measures

Primary outcomes include perceived stress, role clarity, task mastery, and social acceptance. These outcomes will be measured during the first 13 weeks for the intervention group and at week 13 for the control group. All instruments use five-point Likert scales in Swedish, based on questionnaires previously validated in the Swedish context. Secondary outcomes include recovery, intentions to stay, and job satisfaction. These will be measured at months 4, 8, and 12 for the intervention group. The instruments use five- or seven-point Likert scales in Swedish, based on measures previously validated in the Swedish context.

Covariates

Covariates will include variables related to the outcomes such as role clarity, task mastery, social acceptance and demographic factors, such as prior clinical experience before participation in the programme.

Definition of combined measures

Scale scores will be computed by summing items response format (0 - 4 or 0- 6 depending on the instrument).

Missing Data

The extent and pattern of missingness will be described. If indicated, sensitivity analyses may be performed.

Plan of statistical analyses

Statistical analyses will be conducted using SPSS Statistics, with support from experienced researchers and statisticians. All procedures and results will be verified for accuracy. The data will be checked for deviations from normality. The plan is to analyse and report data with descriptive statistics, ANOVA, and χ^2 . This to compare the mean scores of the study variables, including CI and p-values, to determine differences between control and intervention groups. A two-sided significance level of $p = .01$ will be applied. Bonferroni correction to control the family-wise error rate (FWER) will be used, adjusting the conventional threshold of $p = .05$ by dividing it by the number of tests. The effect size of mean differences could be included. To further examine differences between the control and intervention groups, linear regression analysis will be conducted. The models will include covariates. Consort guidelines will be used to support the analysis process.

6. Utilization, Dissemination, and Communication Plan

The interventions are expected to contribute to a sustainable working life for nurses by strengthening competence, reducing stress, and promoting retention. Results will be utilized to inform healthcare policy and organizational practices aimed at improving nurse retention and well-being. Results will be disseminated regionally, nationally, and internationally

through peer-reviewed scientific articles, conference presentations and to stakeholders and health care professionals. The project will result in the production of a doctoral thesis, where findings from all study components will be synthesized. To ensure broader communication, key outcomes will also be shared via media and networks.

References

- Duchscher, J. (2012). *From surviving to thriving. Navigating the first year of professional nursing practice*. Nursing the future, the voice of the new graduates.

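### The planned tests ignore possible correlation within ProDeveloP dialogue groups, so confidence intervals and p-values may be too optimistic

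*Combined protocol and SAP*

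**What the plan says.** **Grouped delivery.** Section 2 (Interventions of ProDeveloP) describes what the programme adds to its 2022 predecessor: "It also included additional components such as four focus areas", followed by "integrated structured reflection facilitated through dialogue groups". The number, size, composition and stability of these groups are not stated.

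**Design and size.** Section 5 (Study design and study population) states: "A quantitative intervention design with a non-randomised design with a two-arm structure is planned". Section 4 (Research participants) expects "Two groups (January 2023 and June 2023), each with 40–50 participants" for the intervention and a control group "with approximately 40-50 participants".

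**Outcomes.** Section 5 (Outcome measures) states: "Primary outcomes include perceived stress, role clarity, task mastery, and social acceptance".

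**Analysis.** Section 5 (Plan of statistical analyses) states: "The plan is to analyse and report data with descriptive statistics, ANOVA, and χ^2". To examine arm differences further, "linear regression analysis will be conducted", with covariates. The same section sets a two-sided level of .01 and also a Bonferroni rule of .05 divided by a number of tests that it does not give. Section 5 (Covariates) does not list dialogue group. The document names no mixed model, cluster-robust variance or ICC.

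**The concern.** Nurses who reflect together on emotional and ethical strain may come to resemble one another on outcomes such as perceived stress and social acceptance. This source of correlation would arise in the intervention arm only, because the dialogue groups are described as an addition to the control programme.

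Ordinary ANOVA and least-squares regression take each nurse as a separate piece of information. With positive within-group correlation, the intervention mean is less precise than they assume. The intervals that the plan promises would then be too narrow and the p-values too small. The chance of a false positive on at least one primary outcome could also pass the 5% that the Bonferroni rule is meant to protect.

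**Working it through.** **The plan's own figure.** The stated level of .01 equals .05/5, but no family of five tests is named. Four primary outcomes give .05/4 = .0125, and all seven named outcomes give .05/7 = .0071. Both .01 and .0125 are therefore carried through.

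**Inputs from the document** (section 4, Research participants; section 5, Outcome measures)
- Intervention arm: 2 × 40–50 = 80–100, midpoint 90.
- Control arm: 40–50, midpoint 45.
- Primary outcomes: 4.

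**Assumed, because the document gives neither**
- Group size m = 6–15, which means 90/15 = 6 to 90/6 = 15 groups.
- ICC = .01–.10.

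**Formulas**
- Design effect, intervention arm only: DE = 1 + (m − 1) × ICC.
- Standard error ratio: R = √[(1/45 + DE/90) / (1/45 + 1/90)] = √[(2 + DE)/3].
- Real per-test error: 2 × P(Z > z/R), with z = 2.576 at .01 and 2.498 at .0125.
- Family-wise rate over four outcomes taken as independent: 1 − (1 − error)⁴.

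**One case in full (m = 10, ICC .05, level .01).** DE = 1 + 9 × .05 = 1.45. R = √(3.45/3) = 1.072. z/R = 2.576/1.072 = 2.402. Per-test error = .0163. Family-wise rate = 1 − (1 − .0163)⁴ = .064.

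| m | ICC | DE | R | Per test at .01 | Family-wise at .01 | Per test at .0125 | Family-wise at .0125 |
|---|---|---|---|---|---|---|---|
| 6 | .01 | 1.05 | 1.008 | 1.1% | 4.2% | 1.3% | 5.2% |
| 10 | .01 | 1.09 | 1.015 | 1.1% | 4.4% | 1.4% | 5.4% |
| 15 | .01 | 1.14 | 1.023 | 1.2% | 4.6% | 1.5% | 5.7% |
| 10 | .05 | 1.45 | 1.072 | 1.6% | 6.4% | 2.0% | 7.7% |
| 15 | .10 | 2.40 | 1.211 | 3.3% | 12.7% | 3.9% | 14.8% |

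**Slack at .01.** Without clustering, four tests at .01 have a family-wise rate of at most 4 × .01 = .040. That bound passes .05 when the per-test error exceeds .0125, that is, when R² > (2.576/2.498)² = 1.0635. This corresponds to DE > 1 + 3 × .0635 = 1.19, so the break-even ICC is .19/(m − 1): about .038 at m = 6, .021 at m = 10 and .014 at m = 15.

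**Simulation check.** Pooled t-tests at .01 were simulated with 20,000 replicates, 45 versus 90 nurses, groups of 9 and ICC .05. They gave about .016 per test. The family-wise rate was .061 with uncorrelated outcomes and .054 with an outcome correlation of .5.

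**Intervention-only means.** Here no unclustered control arm dilutes the effect and R = √DE, from √1.05 = 1.02 to √2.40 = 1.55. This bears on the secondary outcomes, whose stated measurement times (months 4, 8 and 12) are for the intervention arm.

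**Interval width under a corrected analysis.** With g groups, Satterthwaite degrees of freedom are (vT + vC)² / [vT²/(g − 1) + vC²/44], where vT = DE/90 and vC = 1/45. At m = 10, ICC .05 and g = 9 this is about 34. The 99% t-quantile is then about 4.5% larger than at 133 degrees of freedom, and 1.072 × 1.045 = 1.12. Over the range from (m = 6, ICC .01) to (m = 15, ICC .10), intervals widen by about 3% to 36%, compared with 1% to 21% from the standard error ratio alone.

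**The case against.** **The size is assumed.** Group size, ICC and stability of membership are all absent from the document, and at ICC .01 the effect is negligible. Design effects depend on responders per group and participation is voluntary, so non-response would lower them. The four outcomes are probably correlated, which lowers the family-wise rate somewhat, as the simulation shows. All of this stands. It limits the claim about size but leaves the direction of the error unchanged.

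**A reader might infer that the 5% family-wise limit is certainly broken.** The document does not support that. At the stated .01, four tests have slack until the ICC reaches roughly .014–.038 for groups of 15 down to 6. The slack disappears if .01 means .05/5, or nearly so if .05/4 governs. The plan does not say which family applies.

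**A reader might also infer that each group had its own fixed facilitator and constant peers.** Section 2 says only that reflection took place through dialogue groups. If membership changed between sessions, there is no simple nesting, and a random intercept per group would be mis-specified.

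**Other grouping matters too.** One 2022 control intake is compared, without randomisation, with two 2023 intakes. A dialogue-group term does nothing about that. This is correct, and it is a separate issue.

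**Conclusion.** The gap is real: a grouped component is part of the intervention, and every named quantitative method assumes independent nurses. Any positive within-group correlation makes the standard errors too small. How much is not known.

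Under the assumptions listed (45 versus 90 nurses, groups of 6–15, ICC .01–.10), the understatement of the standard error runs from trivial (ratio 1.01) to material (1.21). At the stated .01 level, the family-wise rate over four independent outcomes runs from 4.2%, within the limit, to 12.7%. The central case of groups of 10 and ICC .05 gives a modest excess, at 6.4%. If .0125 is the operative threshold, the range is about 5–15%. The supportable conclusion is that intervals and p-values may be too optimistic and that the 5% limit may not be held. The interval problem does not depend on which multiplicity rule applies.

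**What to change.** **If membership was recorded and stable.** Carry the dialogue-group identifier into the analysis dataset. Analyse the primary outcomes with a partially nested linear mixed model, which SPSS MIXED can fit:
- fixed effects for arm and pre-programme covariates;
- a random intercept for dialogue group in the intervention arm only, with each control as a group of one;
- Satterthwaite or Kenward-Roger degrees of freedom.

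In longitudinal models, nest nurse within dialogue group. Report the number and size of groups and the estimated ICC. If the group variance is estimated as zero, the model returns essentially the ordinary result.

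**If membership was not recorded or was not stable.** Say so in the SAP, and report the arm comparison with a design-effect sensitivity range over stated group sizes and ICCs.

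**In either case.** State the number of tests behind the .01 level.

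**Cost.** The change needs one variable from programme records and a few SAP sentences. That the identifier is on file and can be linked to survey responses is an assumption; the document describes neither. Intervals widen by at least the standard error ratio, and somewhat more because only about 6–15 groups would exist. The change does not address the difference between the 2022 control intake and the two 2023 intervention intakes.

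### No analysis method is specified that handles within-nurse correlation and missed surveys in the intervention arm's longitudinal questions

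*Combined protocol and SAP*

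**What the plan says.** Section 3 asks two questions about change within nurses. Research question 1 reads "What does the development of role clarity, task mastery, social acceptance, and stress look like during the first quarter of employment"; question 2 asks how recovery evolves over the first year.

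The data for both are repeated records on the same people. Section 4 (Design and Data Collection) states that "self-assessments are conducted once a week during the first quarter for the intervention group". Section 5 (Outcome measures) says of the primary outcomes "These outcomes will be measured during the first 13 weeks for the intervention group and at week 13 for the control group", and of the secondary outcomes, recovery among them, "These will be measured at months 4, 8, and 12 for the intervention group".

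Table 1 assigns question 1 "Descriptive statistics, regression analyses" without saying which kind of regression. It assigns the questionnaire parts of questions 2 and 4 (2b and 4a) descriptive statistics, ANOVA and chi-square. The SAP's analysis section lists descriptive statistics, ANOVA, chi-square and linear regression in SPSS, and frames the tests as comparisons of control with intervention. Neither section mentions a mixed model, GEE, repeated-measures ANOVA, cluster-robust errors or a covariance structure.

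On missing data, the SAP will describe extent and pattern, and adds "If indicated, sensitivity analyses may be performed".

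**The concern.** The SAP is meant to cover the self-assessment instruments, yet for most of the intervention arm's records it gives no analysis suited to their structure. The named methods can be read in two ways, and each has a cost.

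- **Records treated as independent.** Linear regression on pooled weekly records, one-way ANOVA across occasions, or chi-square across occasions all count one nurse's surveys as if they came from different nurses. Standard errors are then wrong, in a direction that depends on the term tested.
- **Repeated-measures ANOVA.** This models the correlation, but the SPSS procedure deletes any nurse with a missed occasion. Participation is voluntary, so missed surveys are foreseeable. If stressed nurses skip more often, those who remain are a selected group.

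Leaving the regression undefined also lets the model be chosen after the results are seen, which weakens a plan presented as pre-specified.

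**Working it through.** The plan states no correlation, response rate, standard deviation or power, so it has no figure to reproduce. What follows shows the size of the problem under declared assumptions.

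**Inputs from the documents**
- Occasions: T = 13 weekly surveys; T = 3 follow-ups (months 4, 8, 12).
- Intervention arm: "Two groups (January 2023 and June 2023), each with 40–50 participants", so 80–100 nurses.
- Two-sided level .01 (SAP), critical value 2.576.

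**Assumed**
- Within-nurse correlation ρ = 0.3, 0.5, 0.7.
- Response per survey 95%, 90%, 80%.

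**1. Nurse-level predictor in a pooled model** (for example prior clinical experience, which the SAP lists as a covariate). Design effect DE = 1 + (T − 1)ρ; true SE / naive SE = √DE; actual type I error = 2[1 − Φ(2.576/√DE)].

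| T | ρ | DE | √DE | Type I error at nominal .01 |
|---|---|---|---|---|
| 13 | 0.3 | 4.6 | 2.14 | 0.23 |
| 13 | 0.5 | 7.0 | 2.65 | 0.33 |
| 13 | 0.7 | 9.4 | 3.07 | 0.40 |
| 3 | 0.3 | 1.6 | 1.26 | 0.04 |
| 3 | 0.5 | 2.0 | 1.41 | 0.07 |
| 3 | 0.7 | 2.4 | 1.55 | 0.10 |

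A simulation of pooled least squares on 90 nurses × 13 weeks (4,000 runs per scenario) gave 0.24, 0.33 and 0.40 for the first three rows.

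**2. Time trend in a pooled 13-week model**
- Nurses differ only in level: true SE / naive SE = √(1 − ρ) = 0.84, 0.71, 0.55. The test is too conservative; simulated type I error was 0.005 or less.
- Nurses also differ in slope, with slopes taking a share s of the variance: the squared SE ratio becomes T·s + (1 − ρ − s). At ρ = 0.5:
  - s = 0.10: 1.3 + 0.4 = 1.7, ratio 1.30, type I error 0.05 (simulated 0.04).
  - s = 0.20: 2.6 + 0.3 = 2.9, ratio 1.70, type I error 0.13 (simulated 0.14).
- The ratio passes 1 once s exceeds ρ/(T − 1) = 0.5/12 ≈ 0.04, so modest slope variation is enough to reverse the direction.

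**3. Repeated-measures ANOVA over three follow-ups.** With independent response p per survey, the share of nurses kept is p³.
- p = 0.95: 0.857, or 69–86 of 80–100 nurses.
- p = 0.90: 0.729, or 58–73.
- p = 0.80: 0.512, or 41–51.

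Clustered non-response keeps more. If 80% of nurses respond at 98% and 20% at 58%, overall response is 0.784 + 0.116 = 0.90, and the share complete is 0.8 × 0.98³ + 0.2 × 0.58³ = 0.753 + 0.039 = 0.79, against 0.73 under independence.

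**The case against.** The strongest reply is that this is an omission, not a wrong choice. Table 1's wording for question 1 is generic and does not exclude a mixed model, and the SAP's linear regression is tied to the group comparison. That stands. A reader might infer that the plan commits itself to ordinary least squares on the weekly records, but the documents do not say so.

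Three further inferences are tempting and also go too far.

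- **The control-versus-intervention comparison is invalid.** It is not affected by this point. The SAP gives that comparison its own survey, in early May or December, matched in timing to the single control survey. That is one record per nurse, so within-nurse correlation does not enter.
- **Most nurses would be lost from the weekly analysis.** This would need a 13-occasion repeated-measures ANOVA. Table 1 assigns the weekly question regression, and pooled regression drops missed records, not nurses. The deletion figures above therefore concern the three follow-ups only.
- **Question 4 is equally affected.** It asks about satisfaction, confidence and wish to stay once the programme is over, which one time point could answer. The point reaches 4a only if several follow-ups are analysed together.

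It is also fair that question 1 names no nurse-level predictor and that the SAP's covariates belong to the group-comparison models. The inflated error rates apply only if such a predictor enters a pooled longitudinal model.

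What survives is the gap itself. Questions 1 and 2b ask about change within nurses, and neither reading of the named ANOVA, nor pooled regression, answers them without wrong standard errors or discarded nurses.

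**Conclusion.** The point holds for question 1 and question 2b, and for 4a conditionally. No method accounting for both within-nurse correlation and missed surveys is specified for them.

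The size depends on values the documents do not give. If weekly records are pooled, a nurse-level predictor is tested at an actual level of roughly 0.23–0.40 instead of .01. Over three follow-ups the level is 0.04–0.10. No single direction can be claimed for the time trend: the test is conservative if nurses differ only in level and anti-conservative once slopes vary appreciably. If repeated-measures ANOVA is meant for the follow-ups, between about half and six-sevenths of nurses remain at 80–95% independent response, and more if the same nurses tend to miss surveys.

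This should be corrected, but it does not undermine the between-group result at week 13.

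**What to change.** Amend Table 1 and the SAP's analysis section as follows.

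- **Questions 1 and 2b:** a linear mixed model per outcome (SPSS MIXED, REML) on all available surveys, with time since programme start and intake as fixed effects and a random intercept per nurse.
- **13 weekly occasions:** add a random slope for time, serially correlated residuals, or both, and state the choice and any fallback in advance.
- **Three follow-ups:** use a simpler covariance structure, because three occasions support little more.
- **Categorical outcomes:** use GEE or a mixed logistic or ordinal model in place of chi-square across occasions. The same applies to 4a if several follow-ups are used; otherwise name its single time point.
- **Missing data:** state that the mixed model assumes missingness depends only on observed data, and name at least one sensitivity analysis to that assumption.
- **Group comparison:** state that it uses one survey per nurse at about week 13, so that the two analyses are not confused.

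The gain can be illustrated. With 90 nurses and 10% of weekly surveys missed, the model would use about 0.9 × 13 × 90 = 1,053 of 1,170 records.

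The cost is SAP wording and modest extra analysis, with the same data and software. The document is an update dated February 2026 and the cohorts started in 2023, so the amendment must be dated and disclosed as made after the planned data collection.

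### The control-versus-intervention regression adjusts for three primary outcomes measured after exposure, so its group coefficient is not the total programme effect

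*Combined protocol and SAP*

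**What the plan says.** All references are to the combined protocol and SAP.

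- **Section 5, Covariates:** "Covariates will include variables related to the outcomes such as role clarity, task mastery, social acceptance and demographic factors". Clinical experience before the programme is given as an example of a demographic factor. That timing attaches to the experience, not to the three scales.
- **Section 5, Plan of statistical analyses:** ANOVA and χ² come first, to compare mean scores between the groups. Then: "To further examine differences between the control and intervention groups, linear regression analysis will be conducted". The next sentence is "The models will include covariates". No covariate is assigned to a particular outcome model.
- **Section 5, Outcome measures:** "Primary outcomes include perceived stress, role clarity, task mastery, and social acceptance". On timing: "These outcomes will be measured during the first 13 weeks for the intervention group and at week 13 for the control group".
- **Section 5, Study design and study population:** the design is non-randomised. Controls started in September 2022 and are surveyed in late November 2022. Repeated surveys are said not to be possible for them.
- **Section 2:** the programme adds "four focus areas—role clarity, task mastery, social acceptance" and recovery.
- **Section 3:** the stated aims are to strengthen or improve "role clarity, capacity for action, social acceptance, reduction of stress, and improvement of recovery".

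**The concern.** A covariate in a group comparison should be fixed before exposure, so that adjusting for it removes prior differences between the arms and nothing else. Here three of the four primary outcomes are on the covariate list. They are what the programme sets out to change, and they would be measured in the same survey as the outcome.

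Holding them constant asks how stress differs between two nurses, one from each programme, who already have the same role clarity, task mastery and social acceptance. That is not the question of whether the programme changes stress. If the scales and stress also share causes that are not measured (ward workload, for example), conditioning on the scales can bias the coefficient further, in either direction.

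What is at stake is interpretation. In a non-randomised comparison, readers will tend to trust the adjusted estimate over the crude one. If the group difference shrinks between ANOVA and regression, the natural reading is that confounding has been removed, when part of the programme's own effect may have been removed instead.

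**Working it through.** **Step 1. Can the three scales be baseline scores?** A covariate in a two-arm model must exist in both arms. Controls have one survey, about week 13 of their own programme, and no repeated measures. Section 4 mentions a control measurement before the intervention starts. The November 2022 survey fits that description, because it precedes the 2023 programme, but it is not a pre-exposure measurement for the controls themselves. Early weekly scores exist only in the intervention arm. In the group model the scales are therefore post-exposure.

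**Step 2. Inputs for size.** The documents state no effect size, SD, correlation or power, so there is no figure to reproduce.

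- From the documents: 40–50 controls and 2 × 40–50 = 80–100 intervention nurses, with midpoints 45 and 90; two-sided significance level .01.
- Assumed: every scale, coded so that higher is favourable, shifts by d = 0.5 SD; the within-group correlation ρ is common to all pairs and ranges from 0.2 to 0.7.

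**Step 3. Closed form.** With k scales as covariates,

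adjusted effect = d × [1 − kρ / (1 + (k − 1)ρ)].

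The share kept is (1 − ρ)/(1 + 2ρ) for stress (k = 3), and (1 − ρ)/(1 + ρ) for one scale adjusted for the other two (k = 2). Power uses the residual variance 1 − kρ²/(1 + (k − 1)ρ) and ignores the small variance inflation from group–covariate correlation.

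| ρ | Stress: share kept | Stress: coefficient (SD) | Stress: power | One scale: share kept | One scale: coefficient (SD) |
|---|---|---|---|---|---|
| 0.2 | 0.8/1.4 = 57% | 0.29 | 0.17 | 0.8/1.2 = 67% | 0.33 |
| 0.3 | 0.7/1.6 = 44% | 0.22 | 0.10 | 0.7/1.3 = 54% | 0.27 |
| 0.5 | 0.5/2.0 = 25% | 0.13 | 0.04 | 0.5/1.5 = 33% | 0.17 |
| 0.7 | 0.3/2.4 = 13% | 0.06 | 0.02 | 0.3/1.7 = 18% | 0.09 |

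Without the three scales the coefficient is the full 0.50 SD, with power about 0.57 (0.50 at 40 v 80, 0.62 at 50 v 100).

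**Step 4. If the scales lie on the path to stress.** Assume each shifts by 0.5 SD, ρ = 0.5, and each lowers stress by 0.3 SD per SD. The total effect is then the direct effect − 3 × 0.5 × 0.3 = the direct effect − 0.45. Simulation at 45 v 90 (2,000 runs each) gave:

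| Direct effect | Unadjusted (power) | Adjusted (rejection rate) |
|---|---|---|
| 0 | −0.46 (0.46) | 0.00 (0.01) |
| −0.15 | −0.60 (0.76) | −0.15 (0.07) |
| −0.30 | −0.75 (0.93) | −0.30 (0.38) |

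The adjusted model returns the direct effect. It is zero only when the direct effect is zero.

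**Step 5. Bias from common causes.** Suppose the three scales shift by 0.5 SD, stress does not shift at all, and ρ = 0.5 arises wholly from unmeasured common causes. The adjusted coefficient is 0 − 0.5 × 3(0.5)/(1 + 2 × 0.5) = −0.375 SD, an apparent harm where there is none.

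**Step 6. Precision lost by removing the scales.** Assume shifts of 0.4 SD, ρ = 0.5, 0.25 SD of stress per SD of each scale, and 1:2 allocation.

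- Variance explained by the scales: 0.25² × (3 + 6 × 0.5) = 0.375.
- Variance inflation when they are in the model: 1 + (1/3)(2/3) × 0.4² × 3/(1 + 2 × 0.5) = 1.053, square root 1.026.
- Ratio of interval widths, without to with the scales: √1.375/1.026 = 1.14 if the residual variance is 1; √(1/0.625)/1.026 = 1.23 if the total within-group variance is 1.

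**The case against.** The strongest reply is that the total difference will be reported anyway. The ANOVA is planned first, does not use these covariates, and gives the unadjusted difference; the regression is only a further look. This stands as far as it goes. A reader might infer that the plan leaves no estimate of the whole group difference, and that would be wrong. But the ANOVA makes no adjustment for prior differences between non-randomised cohorts, and the regression is the only analysis that does.

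A reader might also infer that the regression removes the programme effect and will report a result near zero. The documents do not support that. Complete removal requires the programme to work on stress wholly through the three scales. Section 3 lists role clarity, capacity for action, social acceptance, stress and recovery side by side and does not say that the first three reduce stress. What holds without any causal chain is that the part shared with the covariates is taken out.

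Scope is limited too. The SAP does not assign covariates to models, and a scale cannot be its own covariate. Entering all three in the stress model is the natural reading; entering two in the model for the third is possible but not stated. Table 1 lists regression only for research question 1. The secondary outcomes are scheduled for the intervention group alone, so the point should not be extended to them as group comparisons.

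Finally, the relation between the three scales and stress is a legitimate topic. But the SAP states no mediation or direct-effect aim, and it ties the regression to differences between the groups.

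**Conclusion.** The point holds. As written, the only confounder-adjusted group comparison conditions on post-exposure primary outcomes, and its group coefficient cannot be read as the effect of the programme. That follows from the text and needs no assumed numbers. It is clearest for stress, and it applies to each of the other three primary outcomes if the remaining two scales are entered.

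The size is illustrative only. It depends on correlations and effects that the documents do not give, and on all scales shifting equally: about 57% down to 13% of a 0.5 SD stress effect is kept as the correlation rises from 0.2 to 0.7. The loss could be smaller or larger, and unmeasured common causes could push the estimate either way.

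**What to change.** In a dated amendment, replace the covariate text for the group models with wording along these lines:

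> For each control-versus-intervention comparison, the linear regression will include study group and characteristics fixed before the programme started and recorded in both groups: clinical experience before the programme, and [other listed pre-programme characteristics]. Role clarity, task mastery and social acceptance will not be covariates in these models. Any model that relates these scales to stress will be reported separately as an exploratory association or mediation analysis and will not be interpreted as the group effect.

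List the covariates for each outcome. The documents name only prior clinical experience, so the sponsor must confirm what else was recorded in both arms.

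**Cost.** No new data are needed. Intervals for stress would be about 14% to 23% wider under the assumptions in the last step of the working. The document was last reviewed on 2026-02-18, after the 2023 surveys were scheduled, so this is a late change. The amendment should give its reason and say whether any group comparison had already been run. The scale-adjusted model need not be discarded, only relabelled. The change does not cure confounding: controls have no baseline scale scores, so differences beyond the listed characteristics stay unadjusted and should be stated as a limitation.
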